8.4 Participants Trial Duration

Participants will be enrolled on the trial during their stay in the hospital and, following their discharge, will be followed up for up to 12 months. Their trial participation will end when their 12-month follow-up assessment has been completed.

8.5 Trial aims and objectives

Aim

To evaluate the clinical- and cost-effectiveness of early PTP administration versus late PTP administration for adult patients with traumatic brain injury.

8.5.1 Primary objective

Recruit 1512 patients in a randomised trial (150 in the internal pilot, 1362 in the substantive study) to estimate the absolute difference in the proportion of patients developing VTE between the two arms

(early vs late PTP administration).

8.5.2 Secondary objectives

- Compare the consequences of early versus late PTP administration on functional neurological outcome (assessed using the Glasgow Outcome Score Extended) and quality of life using the EQ-5D-5L⁽⁴⁴⁾
- Compare all-cause mortality between the two arms
- Compare intracranial haemorrhage progression and all serious adverse events between the two arms
- Undertake a detailed economic evaluation.

Early and late PTP administration are defined later in the protocol.

The drug / agent administered for pharmacological thromboprophylaxis (PTP) will be based on local hospital policy – any agent listed in Table 1 above is allowed.

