12.1 Definitions

12.1.1 Adverse event (AE)

Any untoward medical occurrence in a participant or clinical trial participant administered a medicinal product which does not necessarily have a causal relationship with this treatment. An adverse event can therefore be any unfavourable and unintended sign (including an abnormal laboratory finding), symptom, or disease temporally associated with using an investigational medicinal product, whether considered related to the investigational medicinal product.

Recording of adverse events must start from the point of Informed Consent regardless of whether a participant has yet received a medicinal product.

The safety profiles of all drugs used for VTE prophylaxis are well established, and due to the pathology of TBI, trial participants will be regularly monitored and assessed in the intensive care environment at regular intervals throughout the trial, over and above routine clinical care. Given the pragmatic nature of the trial and that the potential risk associated with the trial drug is 'no higher than standard care',

only AEs of special interest (AESI) will be recorded on CRF and sent to the coordination centre as listed below.

Adverse events of special interest (AESI) – assessed and reported in accordance with criteria published by the International Society of Thrombosis and Haemostasis. – see Appendix 1.

The following should all be recorded on the AESI form in the eCRF.

- Thrombocytopenia
- Thrombocytosis
- Prosthetic cardiac valve thrombosis
- Cutaneous vasculitis
- Eosinophilia
- Skin reactions
- Angioedema
- Priapism
- Stevens-Johnson syndrome
- Acute generalised exanthematous pustulosis (AGEP)

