12.1.9 Expected Adverse Events/Serious Adverse Events (AE/SAE)

Due to the nature of TBI, affected individuals can often develop surgical and medical complications. Expected systemic or surgical complications associated with TBI will not be recorded as SAEs.

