12.5 Recording and reporting serious adverse events (SAEs) and serious adverse reactions (SARs)

SAEs will not be recorded or reported as part of the trial. Only SAEs for secondary outcome data (ie AESI) will be recorded in the SAE CRF for the duration of the trial.

SAEs should be recorded in the patients normal medical record as part of their routine care as determined by their treating clinician. All SAEs must be assessed by the PI or delegate for causality/relatedness to determine if the event meets the criteria for reporting to the CI and Sponsor as a Serious Adverse Reaction (SAR). See below for SAR reporting requirements.

Only SARS and SUSARs must be reported to the Chief Investigator using the trial-specific SAR reporting form within 24 hours of their event awareness. The Chief Investigator is responsible for ensuring the assessment of all SAEs for expectedness and relatedness is completed and the onward notification of all SARs and SUSARs to the Sponsor immediately but not more than 24 hours after the first notification. The sponsor must keep detailed records of all SARs reported to them by the trial team.

The Chief Investigator is also responsible for prompt reporting of all reportable serious adverse event findings to the competent authority (e.g. MHRA) of each concerned Member State if they could:

- adversely affect the health of participants
- impact on the conduct of the trial
- alter the risk-to-benefit ratio of the trial
- alter the competent authority's authorisation to continue the trial in accordance with Directive 2001/20/EC

For this trial, only Adverse Reactions that are serious (SARs) or unexpected (SUSARS) will require expedited reporting to the Sponsor.

Principal investigators must record and report SARs and SUSARs to the Sponsor within 24 hours of becoming aware of the event using the SAR form provided.

SARs/SUSARs will only be collected and reported during trial treatment

Any/all SAR reports which do not contain the expectedness assessment will be automatically considered as a SUSAR, and be subject to expedited reporting until such time as an expectedness assessment is documented and reported to the CI & Sponsor. Please see section 12.1.6 for the Reference Safety Information to be used in this trial

The completed SAR Reporting form will be emailed to the coordination centre. Details of where to report the SARs can be found on the TOP-TBI SAR Reporting form and the front cover of the protocol.

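### Section 8.5.2 promises a comparison of all serious adverse events, but section 12.5 does not have them recorded, so the objective cannot be met as written

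*Protocol*

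**What the plan says.** Section 8.5.2 lists four secondary objectives. The third is to "Compare intracranial haemorrhage progression and all serious adverse events between the two arms".

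Section 12.5 states: "SAEs will not be recorded or reported as part of the trial". It allows one exception: "Only SAEs for secondary outcome data (ie AESI) will be recorded in the SAE CRF for the duration of the trial". Everything else stays in the hospital notes: "SAEs should be recorded in the patients normal medical record as part of their routine care as determined by their treating clinician". For central reporting it says: "Only SARS and SUSARs must be reported to the Chief Investigator using the trial-specific SAR reporting form within 24 hours".

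Other parts of the safety section point the same way. Section 12.1.1 says that "only AEs of special interest (AESI) will be recorded on CRF and sent to the coordination centre as listed below". Section 12.1.9 adds: "Expected systemic or surgical complications associated with TBI will not be recorded as SAEs". The introduction to section 12 limits central reporting to selected events, and the safety row of the schedule in 11.6 names only AESI and SARs.

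**The concern.** An objective to compare all SAEs needs a record of every such event, in both arms, in the trial database. Section 12.5 tells sites not to make that record. The conflict cannot be left to a statistical analysis plan, which can say how collected data are analysed but cannot create data.

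If it is left alone, the final report will have to drop a stated objective without explanation, recover events from notes at about 20 sites, or present whatever serious-event counts exist as if they met the objective. The last is the worst, because those counts are selective and some depend on having received a dose.

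**Working it through.** The check is a comparison of sections. No stated figure is at issue, and the protocol gives no SAE rate from which to work out a precision.

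1. **What the objective needs.** Section 12.1.4 defines a serious event broadly: death, threat to life, re-admission or a longer stay not attributed to the original trauma, lasting disability, congenital anomaly, or another important medical event. All of these, in both arms and whatever their cause, fall under 8.5.2.

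2. **What the AESI exception supplies.** Sections 12.1.1 and 12.4.4 list ten terms, such as thrombocytopenia, skin reactions and priapism. Sections 8.6.2 and 11.5.2 add major and clinically relevant bleeding, assessed by Appendix 1, and 11.5.2 runs AESI collection to 12 months. The exception is therefore wider than the ten terms, but well short of all SAEs.

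3. **What other outcomes supply.** Collected in both arms regardless of causality are all-cause death (8.6.2, 14.1.1), symptomatic VTE within 30 days and VTE at 90 days (8.6.1, 8.6.2), and haemorrhage progression (8.6.2). Re-admissions come from Hospital Episode Statistics (11.5.2).

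4. **What is left over.** Take a serious infection that prolongs the index admission, survived and judged unrelated to the drug. It can meet 12.1.4. It is not an AESI, a listed outcome, a SAR or a re-admission. Length of stay is recorded, but that does not identify the event. If the site regards it as an expected complication of TBI, 12.1.9 excludes it a second time. It is not in the database in either arm.

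5. **Whether SARs fill the gap.** Section 12.1.2 ties a reaction to an administered dose, and 12.5 collects SARs and SUSARs only while trial treatment lasts. Under 9.3.2 and 9.3.4 the late arm has no prophylaxis for the first 120 hours and may never have any. The opportunity to record a SAR therefore differs between the arms by design.

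6. **Which text is out of line.** Section 12.5, the introduction to section 12, sections 12.1.1 and 12.1.9 and the schedule in 11.6 are consistent with each other. None of the ten secondary outcome measures in 8.6.2 is an all-SAE measure. The wording in 8.5.2 stands alone.

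**The case against.** The strongest defence is that light safety recording is a reasoned choice. The trial is Type A, the agents are licensed and in routine use, and TBI brings many expected complications. The main harms of giving or withholding prophylaxis (bleeding, haemorrhage progression, VTE and death) are named outcomes. All of that stands. It justifies what 12.5 does, but not an objective that 12.5 rules out.

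Three stronger readings are tempting and should not be adopted.

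- A reader might infer that the trial can compare no serious harm other than harm caused by the drug. Steps 2 and 3 show otherwise.
- A reader might infer that SARs are meant to replace SAEs in the arm comparison. The protocol never says so; in 12.5 and 12.6 SARs serve regulatory reporting. Their asymmetry is a reason for a clarifying sentence, not a second error.
- A reader might see a further contradiction in 12.5, since "The Chief Investigator is responsible for ensuring the assessment of all SAEs for expectedness and relatedness is completed" while only SARs and SUSARs are sent to that role. But 12.5 gives the assessment itself to the principal investigator or a delegate, so the sentence can be read as oversight of delegated work. It could be clearer, but it does not require all SAEs to reach the centre.

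**Conclusion.** The objective to compare all SAEs cannot be met as written. The effect is confined to that clause: the primary outcome, the sample size and the outcome measures in 8.6.2 do not depend on it. What the trial may claim does change. It can report on the serious harms it collects, but not on serious adverse events overall. I rate this as moderate.

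Two conditions apply. First, the conclusion takes 12.5 at its word, and no other section provides for wider SAE collection. Second, counting bleeding as comparable between arms assumes that 8.6.2 governs. Item 7 of Appendix 1, read literally, restricts the bleeding population to patients who have had a dose, which would leave out undosed late-arm patients.

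**What to change.** **Main change.** In 8.5.2, replace the reference to all serious adverse events with the events collected in both arms: haemorrhage progression, major and clinically relevant bleeding, other AESI, and death (already a separate objective there, so a cross-reference is enough). Make clear that bleeding is compared in all randomised patients. Add to 12.5 that SAR and SUSAR counts are descriptive and are not an arm comparison, because they require a dose and are collected only during trial treatment. The cost is an amendment of wording and a narrower safety claim. No new data are needed.

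**Alternative, if the sponsor wants to keep the all-SAE objective.** Amend 12.5, with 12.1.1 and 12.1.9 to match, so that SAEs are recorded in both arms whatever the causality or dosing, over one fixed window from randomisation, for example to day 30. The window should not end at discharge: length of stay is itself a post-randomisation outcome, so the arms could be observed for different times. Recording need not mean expedited reporting. The cost is a protocol amendment, a short form and extra site data entry, and it partly reverses the low-burden approach. It should be settled before or early in recruitment, because events missed by then would have to be recovered from notes.

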8.6 Trial outcome measures

8.6.1 Primary outcome measure

Clinically relevant VTE within 30 days from randomisation, including any confirmed diagnosis of symptomatic DVT, pulmonary embolism, or death related to VTE.

The definition of ***clinically relevant*** VTE is as follows:

- Any ***symptomatic*** DVT or PE event where the treating team has made a working diagnosis for a DVT or PE based on symptoms and or clinical signs and subsequently investigations requested to verify the diagnosis (e.g., ultrasound / CT pulmonary angiogram (CTPA)).

DVT or PE occurrence

Symptomatic DVT or PE will be investigated as per standard clinical practice either by compression Doppler ultrasound of the femoral and popliteal veins or CTPA, as appropriate.

8.6.2 Secondary outcome measures

- Proximal DVT at asymptomatic screening ultrasound (*only relevant for sites where they undertake screening ultrasound as part of routine clinical practice*)
- Progression of intracranial haemorrhage within 14 days after randomisation requiring neurosurgical intervention
- Progression of intracranial haemorrhage on routinely performed imaging
- Adverse events, of special interest (AESI) including major and clinically relevant bleeding events (bleeding events are assessed and reported in accordance with criteria published by the International Society of Thrombosis and Haemostasis) (see Appendix 1)
- VTE at 90 days
- 7-day, 30-day, and 12-month mortality
- Glasgow Outcome Scale-Extended (GOS-E) at 6 and 12 months

- Quality of life (EQ5D-5L) at Day 30 or discharge, 6 and 12 months
- Length of stay of index admission
- Economic analysis (see section 16.5)

Given patients with TBI are prone to VTE events, some hospital practices undertake a screening ultrasound to investigate for asymptomatic DVTs. Sites will be allowed to perform screening ultrasound at their discretion; however, this trial will only include **asymptomatic proximal DVT** diagnosed by ultrasound. A proximal DVT is defined as a DVT that is in the popliteal, femoral or iliac veins. A DVT that is located below the knee and is confined to the calf veins (peroneal, posterior, anterior tibial, and muscular veins) without a proximal component will not be recorded. This is because up to 25% of patients admitted to an intensive care environment can have asymptomatic distal DVTs that are of no clinical relevance.

The trial will allow any **asymptomatic proximal DVT** as part of asymptomatic screening ultrasound diagnosed from the day of randomisation up until day 29 post randomisation. This will be recorded as a secondary outcome.

9. Selection and withdrawal of participants

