6.1 Background

Every year in the UK, an estimated 1.4 million people suffer a Traumatic Brain Injury (TBI) and 200,000 people with TBI are admitted to hospital (1). Following a TBI, patients are at considerable risk of morbidity and mortality for several reasons, including the development of venous thromboembolism (VTE) (2). The most common types of VTE are deep vein thrombosis (DVT) and pulmonary embolism (PE). These problems can complicate recovery from TBI, lead to a longer-term reduction in quality of life and can occasionally be fatal.

Recent systematic reviews have reported a VTE incidence rate following TBI of approximately 10% (3–5). The aetiology of provoked VTE in TBI patients is multifactorial, including prolonged immobility, motor deficits, presence of extracranial injuries, inflammatory cascades, and hyper-coagulability (5–7). The prothrombotic state following traumatic injury has been attributed to many factors, including decreased levels of functional protein C and abnormal antithrombin levels (8).

VTE events are of great clinical concern. TBI patients already face complex recovery from their initial injury, and additional complications, including VTE, have been shown to worsen their outcomes by lengthening hospital stays and reducing their likelihood of being discharged home (9). Therefore, developing effective strategies to prevent VTE in patients with TBI is essential and a priority in this patient group.

In hospitalised patients, national guidelines recommend using mechanical VTE prophylaxis and early initiation of pharmacological VTE prophylaxis (PTP) for appropriate patient populations (10). In a broad population, this has reduced VTE-related deaths up to 90 days after discharge by 15.4% in the last 12 years (11). However, there are no clear national guidelines on VTE prophylaxis following TBI, including PTP; risk assessment models have not been validated in these patients (12,13). This lack of evidence is also reflected in the Brain Trauma Foundation guidelines (4th edition), stating there is insufficient Level I or II evidence to make recommendations on the timing of PTP in TBI (13). Recent work in patients without TBI suggests a lower bar for prescribing thromboprophylaxis could improve outcomes and make the best use of NHS resources (9,14).

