11.5 Trial assessments

11.5.1 Timing of assessments

Participants will be monitored as per routine clinical practice until discharge and thereafter at 30 days (+/- 5 days), 90 days (+/- 15 days), 6 months and 12 months (+/- 1 month) to score clinical outcomes.

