11.5.2 Assessments at time point

- Adverse events of special interest (AESI) during treatment and follow up timepoints up to 12 months. including major and clinically relevant bleeding events
- Asymptomatic DVT assessment with an ultrasound scan during hospital stay (*only relevant for all sites that perform screening ultrasound as part of routine clinical practice*)
- Assessment for VTE during hospital admission, 30 days and 90 days
- Progression of intracranial haemorrhage on routinely performed imaging within 14 days after randomisation requiring neurosurgical intervention
- Quality of life (EQ5D-5L) at Day 30 or discharge, 6 and 12 months
- Mortality at 7-days, 30 days and 12 months
- Glasgow Outcome Scale-Extended (GOS-E) at 6 and 12 months
- Length of stay of index admission
- Economic analysis at 12 months

Method of follow-up

Prospective follow-up data (at 30 days - primary endpoint), 90 days, 6- and 12-months post-enrolment) will be collected electronically via email or online formats such as Qualtrics or MS Forms or via postal questionnaires or telephone interviews by blinded study personnel if participants cannot complete forms electronically/return postal questionnaires. The questionnaires will include questions on any longer-term effects of VTE, the extended Glasgow Outcome Scale (GOSE, only 6 and 12 month FU) and EQ-5D-5L questionnaire (30 days, 6- and 12-month FU). Re-admission and out-patient data will be captured from Hospital Episode Statistics (HES) data.

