11.6 Table for schedule of assessments (Table 2)

	Screening/ Baseline (within 72 hours of TBI)	Treatment Phase (within 72 hours of TBI OR >120 hours of TBI)	Day 7	Day 14	Day 30 (+/- 5 days) OR Discharge	Follow up phase		
						Day 90 (+/- 15 days)	6 months (+/- 1 month)	12 months (+/- 1 month)
Eligibility assessment	X							
Informed consent	X							
Randomisation	X							
IMP administration		X						
Safety assessments (AESI/SARs)	X	X	X	X	X	X	X	X
Intracranial haemorrhage				X				
Mortality			X		X			X
VTE occurrence	X				X	X		
GOSE							X	X
EQ-5D-5L					X		X	X
Economic evaluation								X

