15.6 Economic evaluation

An economic analysis will be undertaken to compare the cost-effectiveness of early PTP versus late PTP, and a 12-month trial economic evaluation will be conducted. Costs will be estimated from the viewpoint of the NHS and include LMWH, hospital admissions, potentially related medication use, investigations, readmissions and outpatient appointments using data from HES. The main outcome

measure will be the EQ-5D-5L (44) at day 30/discharge, 6 and 12-month follow-up, enabling Quality Adjusted Life Year (QALY) scores to be estimated. Based on a pre-specified Health Economic Analysis Plan (HEAP), the analysis will be undertaken to estimate the incremental cost and incremental effect (QALY gain) associated with early PTP compared to late PTP. Assuming dominance does not occur (where one option is estimated to be more effective and less costly than the other option), the incremental cost-effectiveness ratio (ICER) of early PTP will be estimated and assessed concerning a range of cost-effectiveness thresholds e.g., £20,000-£30,000 per QALY has been recommended by NICE. The associated level of uncertainty will also be characterised by estimating the cost-effectiveness acceptability curve / conducting sensitivity analysis. This methodological approach has been adopted in a previous trial of TBI patients (37) and will enable recommendations as to the cost-effectiveness of early PTP to be made.

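### The first EQ-5D-5L is timed at day 30 or discharge in most of the protocol and at 30 days in one place, with no rule for choosing, so the first quality-of-life value has no single meaning

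*Protocol*

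**What the plan says.** The first EQ-5D-5L is placed at one of two times in five places:

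- Section 8.6.2 lists "Quality of life (EQ5D-5L) at Day 30 or discharge, 6 and 12 months".
- The trial flow chart (section 5) and the assessment list in 11.5.2 use the same wording.
- Table 2 (11.6) puts the first EQ-5D-5L cross in a column headed "Day 30 (+/- 5 days) OR Discharge". It has no cross at screening or baseline.
- Section 15.6 carries the choice into the economic evaluation. Of its principal endpoint it says: "measure will be the EQ-5D-5L (44) at day 30/discharge, 6 and 12-month follow-up, enabling Quality Adjusted Life Year (QALY) scores to be estimated".

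The follow-up method in 11.5.2 differs. It schedules the "EQ-5D-5L questionnaire (30 days, 6- and 12-month FU" and does not mention discharge. Section 11.5.1 has participants monitored to discharge and "thereafter at 30 days (+/- 5 days), 90 days (+/- 15 days), 6 months and 12 months (+/- 1 month".

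No section says which of the two times applies to which participant, or whether the earlier or the later is meant.

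Two other statements matter. Section 8.6.2 makes "Length of stay of index admission" a secondary outcome. Section 6.1 says that complications, VTE among them, "have been shown to worsen their outcomes by lengthening hospital stays and reducing their likelihood of being discharged home".

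**The concern.** Discharge happens after randomisation. If it fixes the date of the questionnaire, one participant is scored a week after injury and another at a month, or later still if a late discharge counts. Quality of life can be expected to change quickly over those weeks, so the scores are not on a common footing.

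By the protocol's own account, VTE affects length of stay. An intervention that changes the VTE rate can therefore change when patients are measured as well as how they are. A between-arm difference at this time point could then mix treatment effect with a difference in timing.

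Comparing EQ-5D-5L between arms is a stated secondary objective (8.5.2), and the same value feeds the QALYs. With no baseline EQ-5D-5L, it is the only utility observation before month 6.

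**Working it through.** **Inputs.** The protocol gives no EQ-5D values and no lengths of stay, so there is no figure of its own to reproduce here. From the protocol come the 5-point VTE reduction (10% to 5%, section 15.3) and the 5-day window around day 30. Everything else below is assumed and shown as a range.

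**1. Effect of timing on one patient.** Assume a recovery curve that is the same in both arms, so that there is no treatment effect:

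u(t) = u0 + (0.65 − u0) × (1 − exp(−t/τ)), with 0.65 the value approached by about 6 months.

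Example for the slow curve (u0 = 0.3, τ = 90 days): u(7) = 0.326 and u(30) = 0.399, a difference of −0.073.

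| Assumed curve | Day 7 minus day 30 | Day 14 minus day 30 | Day 60 minus day 30 | Day 35 minus day 25 |
|---|---|---|---|---|
| u0 0.1, τ 30 days | −0.233 | −0.143 | +0.128 | 0.068 |
| u0 0.2, τ 60 days | −0.128 | −0.083 | +0.107 | 0.046 |
| u0 0.3, τ 90 days | −0.073 | −0.049 | +0.071 | 0.028 |

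The day-60 column applies only if a later discharge is allowed to replace day 30. The last column is the spread that remains with a fixed day 30 and its window, about 0.03 to 0.07.

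**2. Weight of the first value in the QALYs.** Use linear interpolation, with 6 months as 182.5 days.

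- With a separate assumed value at day 0: [30/2 + (182.5 − 30)/2] / 365.25 = 91.25/365.25 = 0.250.
- With the first value carried back flat to day 0: [30 + (182.5 − 30)/2] / 365.25 = 106.25/365.25 = 0.291.

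The 6-month value anchors the other end of that interval.

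**3. QALY shift for one patient discharged and scored on day 7**, relative to a day-30 score, using the assumed day-0 value:

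| Assumed curve | Score treated as day 30 | Score placed at its actual date |
|---|---|---|
| u0 0.1, τ 30 days | −0.233 × 0.250 = −0.058 | −0.041 |
| u0 0.2, τ 60 days | −0.128 × 0.250 = −0.032 | −0.018 |
| u0 0.3, τ 90 days | −0.073 × 0.250 = −0.018 | −0.009 |

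The right-hand column compares the area [½(u(0) + u(d))·d + ½(u(d) + u(182.5))·(182.5 − d)] / 365.25 at d = 7 and at d = 30. Using the actual date reduces the shift but does not remove it, because a straight line from day 7 to month 6 follows a curved recovery less well than one from day 30. A fixed day 30 also has interpolation error, but it does not depend on the discharge date.

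**4. Shift between arms through VTE alone.** Assume 3 to 14 extra days in hospital per VTE and scoring around day 14, where the curves rise by 0.0033 to 0.0113 per day.

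- Shift in mean stay: 0.05 × 3 = 0.15 days to 0.05 × 14 = 0.7 days.
- Spurious EQ-5D difference: 0.15 × 0.0033 = 0.0005 to 0.7 × 0.0113 = 0.008.
- In QALYs, at weight 0.250: about 0.0001 to 0.002.

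For comparison, a 5-day shift in mean stay from any cause would give 0.016 to 0.053 on EQ-5D.

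**The case against.** **A benign reading.** The Table 2 column also holds mortality and VTE occurrence. These have fixed 30-day outcomes and could not be completed at an early discharge, so the heading may be no more than a visit label. The follow-up method already sends the EQ-5D-5L at 30 days. On that reading discharged patients do get a day-30 score, and the fault is one of wording. This is possible, but 8.6.2, the 11.5.2 list and 15.6 offer the choice for the EQ-5D-5L itself, and nothing tells a site not to treat a discharge form as completing the item.

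**The analysis plan may deal with it.** Section 15.6 places the economic analysis in a separate plan ("Based on a pre-specified Health Economic Analysis Plan (HEAP"), which is not shown and may use actual dates. That would help, as step 3 shows. It cannot supply a day-30 value that was never collected.

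**Size.** A reader might infer that the timing effect could cancel the QALY gain expected from early PTP. A 2-day shift in mean scoring date at an assumed 0.01 per day gives 0.02 × 0.250 = 0.005 QALY, equal to a 5-point VTE reduction at an assumed 0.1 QALY per event (0.05 × 0.1 = 0.005). The documents do not support this. Through VTE alone, a 2-day shift needs 2/0.05 = 40 extra days per event. If the earlier of the two times applies, scoring stops at day 30 to 35, and the mean shift stays below 0.05 × 30 = 1.5 to 0.05 × 35 = 1.75 days. This objection stands.

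**Direction.** A reader might also infer that the bias must run against the arm with the shorter stay. That requires discharge to replace day 30, and utility to rise with time regardless of how ready the patient is to go home. A patient who leaves early because of a good recovery need not score lower, and haemorrhage progression could move stay either way. This objection stands too.

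**Conclusion.** The protocol contradicts itself on when the first EQ-5D-5L is collected and gives no rule to settle it. Taken literally, the majority wording ties the date to a trial outcome. The main consequences are added noise and a first comparison without a single meaning: 0.07 to 0.23 between day 7 and day 30 for the same patient, against 0.03 to 0.07 across the fixed day-30 window. An arm-dependent shift is possible but probably small if VTE is the only route, and its sign is not established.

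All these sizes rest on assumed recovery curves, assumed extra days per VTE and linear interpolation. The contradiction in the collection rule does not. The scope is one of three EQ-5D-5L time points, plus its share of the QALYs. The 6- and 12-month scores and the primary outcome are not affected. It is worth correcting because it touches a stated secondary objective and the main economic outcome, and because the problem arises at data collection.

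**What to change.** Set the first EQ-5D-5L at day 30, within 5 days either side, from randomisation for every surviving participant, whether in hospital or not. Make the wording identical in the flow chart, 8.6.2, the assessment list and follow-up method in 11.5.2, Table 2 and 15.6. Record the completion date and use it in the QALY calculation. If a discharge score is wanted, define it as an additional dated measurement that never replaces day 30.

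The cost is mainly redrafting: participants are already followed up at 30 days for the primary endpoint, and the follow-up method already includes the questionnaire then. The downside is slightly more non-response than with a form completed before the patient leaves.
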